#### 5.4.2 Supportive Care Guidelines specific to sEphB4-HSA

sEphB4-HSA is associated with hypertension which can be properly managed medically and as such would not require treatment delays or discontinuation. The following guidelines are provided for supportive care.

- **Hypertension**

This is an expected class effect adverse event. All blood pressure measurements should be made after the patient has been in a supine position for 10 minutes or longer.

- Patients with grade 2 hypertension as evidenced by two or more different measurements that are at least one hour apart should be initiated on antihypertensive therapy per the treating physician.
- In the case of a first occurrence of grade 3 asymptomatic hypertension, patients may continue on treatment while their antihypertensive therapy is optimized. A second occurrence of grade 3 hypertension despite antihypertensive therapy would require holding treatment with sEphB4-HSA until hypertension returns to  $\leq$  grade 2 at which point treatment can be resumed with one dose reduction.

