#### Dose Modification Guidelines for sEphB4-HSA-Related Adverse Event

Toxicity	Hold Treatment For Grade	Timing for Restarting Treatment	Discontinue Subject
Unmanageable  non-hematologic toxicity other than alopecia	3-4	
Toxicity resolves to Grade 0-1 or baseline, one dose level reduction.
 
Patients with toxicities that are manageable with supportive therapy may not require dose reductions (for example, patients with Grade 3-4 nausea, vomiting or diarrhea must have persistent toxicity despite having received optimal supportive therapy in order to require a dose reduction). Patients with <math>\geq</math> Grade 3 electrolyte abnormalities, if easily managed medically (return to Grade 2 or less within 72 hours), do not require a dose reduction.
	Treatment can be continued with supportive management as described in 5.6.1
AST, ALT	2	
Subjects who experience a grade 2 AST and or ALT will have subsequent doing held until the AST/ALT return to grade 0/1 and then can resume the prior dose, however, if the return to grade 0/1 takes longer than 7 days, the subject will be treated at a 1 level dose reduction
 
Grade 3 AST and/or ALT that represents at least a two grade increase from baseline or <math>\text{AST/ALT} \geq 10 \times \text{ULN}</math> –hold therapy, recheck weekly, initiate retreatment when resolved to baseline with one dose level reduction.
	Toxicity does not resolve within 12 weeks of last dose.
	3-4	Permanently discontinue (see exception below) 	Permanently discontinue
Hypertension 	2	Initiate antihypertensive drugs	Treatment can continue while antihypertensive drugs are initiated

Toxicity	Hold Treatment For Grade	Timing for Restarting Treatment	Discontinue Subject
	3	First occurrence, if asymptomatic and on antihypertensive therapy, may continue treatment, and optimize antihypertensive therapy.  Second occurrence, despite antihypertensive therapy, hold until grade < 3, one dose level reduction	Treatment can continue while antihypertensive drugs are initiated
	4	Permanently discontinue sEphB4-HSA	Permanently discontinue sEphB4-HSA
Thrombocytopenia	3-4	Toxicity resolves to Grade 0-1, one dose level reduction	Toxicity does not resolve within 12 weeks of last dose.
Neutropenia	4	Toxicity resolves to Grade 0-1, one dose level reduction	Treatment can continue with GCSF support

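### Section 5.4.2 opens by saying that sEphB4-HSA hypertension needs no delay or discontinuation, which contradicts the dose table's grade 4 stop and the second grade 3 hold required in both sections

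*Combined protocol and SAP*

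**What the plan says.** Two places in the protocol govern hypertension on sEphB4-HSA.

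Section 5.4.2 (supportive care specific to sEphB4-HSA) describes it as "hypertension which can be properly managed medically and as such would not require treatment delays or discontinuation". It then states "The following guidelines are provided for supportive care" and gives two bullets. The first starts antihypertensive treatment at grade 2. The second covers grade 3: "In the case of a first occurrence of grade 3 asymptomatic hypertension, patients may continue on treatment while their antihypertensive therapy is optimized". It continues: "A second occurrence of grade 3 hypertension despite antihypertensive therapy would require holding treatment with sEphB4-HSA" until the event is back to grade 2 or lower, with one dose reduction on resumption. There is no grade 4 bullet.

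The sEphB4-HSA dose modification table in section 5.2.1.3 has rows for hypertension grades 2, 3 and 4. At grade 3 the restart column reads "First occurrence, if asymptomatic and on antihypertensive therapy, may continue treatment, and optimize antihypertensive therapy", followed by a hold and one dose level reduction at a second occurrence. The discontinuation column of the same grade 3 row reads "Treatment can continue while antihypertensive drugs are initiated", which repeats its grade 2 entry. At grade 4 both columns read "Permanently discontinue sEphB4-HSA".

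**The concern.** The opening sentence of 5.4.2 rules out both delay and discontinuation and is not tied to any grade. Further on, the protocol prescribes a delay (second grade 3) and a discontinuation (grade 4) for the same adverse event. A reader who relies on that sentence and a reader who relies on the table would treat a grade 4 event differently.

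This matters for two reasons. Section 5.4.2 describes hypertension as an expected effect of the drug class, so the rules are likely to be consulted, and grade 4 is by the protocol's own grading the life-threatening level. In addition, section 4.2.3.1 measures tolerability by discontinuation for treatment-related toxicity, and the toxicity rule in section 8.2 counts discontinuations before the third course. Instructions that differ on when a drug is stopped make those counts depend on which page was followed.

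**Working it through.** No arithmetic applies: the point rests on no rate, error level or sample size. The check is a grade-by-grade comparison of the two sections.

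| Event | 5.4.2 opening sentence | 5.4.2 bullets | Dose table, 5.2.1.3 | Result |
|---|---|---|---|---|
| Grade 2 | No delay or stop | Start antihypertensives | Start antihypertensives; treatment can continue | No conflict |
| First grade 3, asymptomatic | No delay or stop | May continue while therapy is optimized | Restart column: may continue if already on therapy. Discontinuation column: may continue while drugs are being started | Condition differs within the table row; not stated outright in 5.4.2 |
| Second grade 3, despite therapy | No delay or stop | Hold to grade 2 or lower, one reduction | Hold to below grade 3, one reduction | Bullet and table agree; opening sentence contradicts both |
| Grade 4 | No delay or stop | Nothing stated | Permanent discontinuation of sEphB4-HSA | Opening sentence contradicts the table; no bullet resolves it |

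Reading across the rows:

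1. **Grade 4.** This is the only level at which the dispute is about discontinuation. The competing instructions are to continue (opening sentence) or to stop (table).
2. **Second grade 3.** The two specific rules are the same, since below grade 3 means grade 2 or lower and each carries one reduction. The conflict is between those rules and the opening sentence, so 5.4.2 contradicts itself as well as the table.
3. **First grade 3, asymptomatic.** A patient not yet on antihypertensives fails the condition in the table's restart column but fits its discontinuation column, which speaks of drugs being initiated. The two columns of one row do not describe the same patient.
4. **Precedence.** Section 5.4.1 points readers to 5.2.1 for dose modification, but it does so among guidelines for events related to pembrolizumab. Section 5.4.2 has no such pointer, and neither section says which governs if they differ.

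The hypertension entry in the table carries a footnote marker (3) whose text does not appear in the copy reviewed. No weight is placed on that.

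**The case against.** The strongest reply is that dose action belongs to 5.2.1.3, which makes withholding per its table mandatory, while 5.4.2 offers supportive-care guidance. On that view, silence on grade 4 in 5.4.2 is no contradiction, and a careful investigator would follow the table. The opening sentence might also be read as covering only such hypertension as proves manageable. Much of this is fair: silence alone would not be an error, and most readers would probably turn to the table at grade 4. But 5.4.2 is not merely silent. It makes a general statement about delay and discontinuation, sets no grade at which that statement ceases to apply, and itself gives a hold and a dose reduction, so it cannot be set aside as containing no dose instructions.

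Four stronger readings are tempting but not supported.

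- **That one and the same patient could be continued, held or stopped.** At any one grade at most two instructions compete: continue or stop at grade 4, continue or hold at a second grade 3.
- **That 5.4.2 as a whole denies any need for a hold.** Its own second bullet requires one.
- **That 5.4.2 and the table apply materially different rules to a first asymptomatic grade 3 event.** Optimizing a patient's therapy largely presupposes that the patient is on it. The clearer mismatch is inside the table row, and even that may be grade 2 wording carried down under a heading about discontinuation.
- **That a symptomatic first grade 3 event has no rule at all.** Grade 3 is listed under the column of grades for which treatment is held, so the asymptomatic case can be read as an exception to a hold. The table's general row for unmanageable grade 3-4 non-hematologic toxicity might also apply, and footnote 3 is unseen. Which row applies needs confirming; a gap is not established.

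**Conclusion.** The point holds as an internal contradiction. The opening sentence of 5.4.2 cannot stand alongside the grade 4 row of the dose table, or alongside the second grade 3 hold in that table and in 5.4.2 itself. The first grade 3 condition is a lesser inconsistency, mainly between two columns of one row.

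Its size cannot be expressed as a number. A reader might infer a sizeable effect on the probability of crossing the toxicity boundary in section 8.2, but the documents do not support one. They give no hypertension rate. Only grade 4 events set discontinuation against no discontinuation, since a hold is not a discontinuation, so such an effect would need an assumed frequency of grade 4 hypertension before the third course, and section 4.2.2 reports all dose levels of sEphB4-HSA as well tolerated with no dose-limiting toxicity. The table's grade 4 rule also names sEphB4-HSA alone, so it is not clear that stopping it would count as treatment discontinuation under 8.2. Crossing the boundary would in any case trigger a review of toxicity, not an automatic stop.

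Sample size, error rates and power are unaffected. The case for correction rests on consistent handling of a severe event and on the low cost of the change. The conclusion assumes that footnote 3 does not already reconcile the passages.

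**What to change.** Reconcile the opening sentence of 5.4.2 with the hypertension rows of the dose table in 5.2.1.3 and with 5.4.2's own bullets, so that each of the following carries one instruction, worded alike in both sections:

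- a first grade 3 event, with a single stated condition on antihypertensive therapy used in both columns of the table and in 5.4.2;
- a second grade 3 event;
- a grade 4 event.

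At the same time, check the text of footnote 3 and confirm which row covers a symptomatic first grade 3 event. Which passage yields, and what the clinical rule should be, is for the sponsor's clinical team; this review takes no position on either.

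The cost is protocol wording in 5.2.1.3 and 5.4.2. No analysis, sample size or data collection changes.

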## 5.5 Diet/Activity/Other Considerations

### 5.5.1 Diet

Subjects should maintain a normal diet unless modifications are required to manage an AE such as diarrhea, nausea or vomiting.

### 5.5.2 Contraception

Pembrolizumab may have adverse effects on a fetus in utero. Furthermore, it is not known if pembrolizumab has transient adverse effects on the composition of sperm.

For this trial, male subjects will be considered to be of non-reproductive potential if they have azoospermia (whether due to having had a vasectomy or due to an underlying medical condition).

Female subjects will be considered of non-reproductive potential if they are either:

(1) postmenopausal (defined as at least 12 months with no menses without an alternative medical cause; in women <45 years of age a high follicle stimulating hormone (FSH) level in the postmenopausal range may be used to confirm a post-menopausal state in women not using hormonal contraception or hormonal replacement therapy. In the absence of 12 months of amenorrhea, a single FSH measurement is insufficient.);

OR

(2) have had a hysterectomy and/or bilateral oophorectomy, bilateral salpingectomy or bilateral tubal ligation/occlusion, at least 6 weeks prior to screening;

OR

(3) has a congenital or acquired condition that prevents childbearing.

Female and male subjects of reproductive potential must agree to avoid becoming pregnant or impregnating a partner, respectively, while receiving study drug and for 120 days after the last dose of study drug by complying with one of the following:

(1) practice abstinence† from heterosexual activity;

OR

(2) use (or have their partner use) acceptable contraception during heterosexual activity.

**Acceptable methods of contraception are‡:**

Single method (one of the following is acceptable):

- intrauterine device (IUD)

- vasectomy of a female subject's male partner
- contraceptive rod implanted into the skin

Combination method (requires use of two of the following):

- diaphragm with spermicide (cannot be used in conjunction with cervical cap/spermicide)
- cervical cap with spermicide (nulliparous women only)
- contraceptive sponge (nulliparous women only)
- male condom or female condom (cannot be used together)
- hormonal contraceptive: oral contraceptive pill (estrogen/progestin pill or progestin-only pill), contraceptive skin patch, vaginal contraceptive ring, or subcutaneous contraceptive injection

†Abstinence (relative to heterosexual activity) can be used as the sole method of contraception if it is consistently employed as the subject's preferred and usual lifestyle and if considered acceptable by local regulatory agencies and ERCs/IRBs. Periodic abstinence (e.g., calendar, ovulation, sympto-thermal, post-ovulation methods, etc.) and withdrawal are not acceptable methods of contraception.

‡If a contraceptive method listed above is restricted by local regulations/guidelines, then it does not qualify as an acceptable method of contraception for subjects participating at sites in this country/region.

Subjects should be informed that taking the study medication may involve unknown risks to the fetus (unborn baby) if pregnancy were to occur during the study. In order to participate in the study subjects of childbearing potential must adhere to the contraception requirement (described above) from the day of study medication initiation (or 14 days prior to the initiation of study medication for oral contraception) throughout the study period up to 120 days after the last dose of trial therapy. If there is any question that a subject of childbearing potential will not reliably comply with the requirements for contraception, that subject should not be entered into the study.

### 5.5.3 Use in Pregnancy

If a subject inadvertently becomes pregnant while on treatment with pembrolizumab, the subject will immediately be removed from the study. The site will contact the subject at least monthly and document the subject's status until the pregnancy has been completed or terminated. The outcome of the pregnancy will be reported to the Sponsor, Vasgene Therapeutics and to Merck without delay and within 24 hours to the Sponsor and within 2 working days to Merck and Vasgene Therapeutics if the outcome is a serious adverse experience (e.g., death, abortion, congenital anomaly, or other disabling or life-threatening complication to the mother or newborn).

The study investigator will make every effort to obtain permission to follow the outcome of the pregnancy and report the condition of the fetus or newborn to the Sponsor. If a male subject impregnates his female partner the study personnel at the site must be informed immediately and the pregnancy reported to the Sponsor, Vasgene Therapeutics and to Merck and followed as described above and in Section 7.2.2.

#### **5.5.4 Use in Nursing Women**

It is unknown whether pembrolizumab and sEphB4-HSA is excreted in human milk. Since many drugs are excreted in human milk, and because of the potential for serious adverse reactions in the nursing infant, subjects who are breast-feeding are not eligible for enrollment.

### **5.6 Subject Withdrawal/Discontinuation Criteria**

Subjects may withdraw consent at any time for any reason or be dropped from the trial at the discretion of the investigator should any untoward effect occur. In addition, a subject may be withdrawn by the investigator or the Sponsor if enrollment into the trial is inappropriate, the trial plan is violated, or for administrative and/or other safety reasons. Specific details regarding discontinuation or withdrawal are provided in Section 7.1.4 – Other Procedures.

A subject must be discontinued from the trial for any of the following reasons:

- The subject or legal representative (such as a parent or legal guardian) withdraws consent.
- Confirmed radiographic disease progression

*Note:* For unconfirmed radiographic disease progression, imaging should be repeated after 2 additional cycles of study treatments in order to confirm progressive disease.

*Note:* A subject may be granted an exception to continue on treatment with confirmed radiographic progression if clinically stable or clinically improved,

- Unacceptable adverse experiences as described in Section 5.2.1.2
- Intercurrent illness that prevents further administration of treatment
- Investigator's decision to withdraw the subject
- The subject has a confirmed positive serum pregnancy test
- Noncompliance with trial treatment or procedure requirements
- The subject is lost to follow-up
- Completed 24 months of uninterrupted treatment with pembrolizumab or 35 administrations of study medication, whichever is later.

*Note: 24 months of study medication is calculated from the date of first dose. Subjects who stop pembrolizumab after 24 months may be eligible for up to one year of additional study treatment if they progress after stopping study treatment provided they meet the requirements detailed in Section 7.1.5.5*

- Administrative reasons

The End of Treatment and Follow-up visit procedures are listed in Section 6 (Protocol Flow Chart) and Section 7.1.5 (Visit Requirements). After the end of treatment, each subject will be followed for 30 days for adverse event monitoring (serious adverse events will be collected for 90 days after the end of treatment as described in Section 7.2.3.1). Subjects who discontinue for reasons other than progressive disease will have post-treatment follow-up for disease status until disease progression, initiating a non-study cancer treatment, withdrawing consent or becoming lost to follow-up. After documented disease progression each subject will be followed by telephone for overall survival until death, withdrawal of consent, or the end of the study, whichever occurs first.

### **5.6.1 Discontinuation of Study Therapy after CR**

Discontinuation of treatment may be considered for subjects who have attained a confirmed CR that have been treated for at least 24 weeks with pembrolizumab and had at least two treatments with pembrolizumab beyond the date when the initial CR was declared. Subjects who then experience radiographic disease progression may be eligible for up to one year of additional treatment with pembrolizumab via the Second Course Phase at the discretion of the investigator if no cancer treatment was administered since the last dose of pembrolizumab, the subject meets the safety parameters listed in the Inclusion/Exclusion criteria, and the trial is open. Subjects will resume therapy at the same dose and schedule at the time of initial discontinuation. Additional details are provided in Section 7.1.5.5.

### **5.7 Subject Replacement Strategy**

Patients who are deemed not evaluable for response will be replaced

### **5.8 Clinical Criteria for Early Trial Termination**

Early trial termination will be the result of the criteria specified below:

1. Quality or quantity of data recording is inaccurate or incomplete
2. Poor adherence to protocol and regulatory requirements
3. Incidence or severity of adverse drug reaction in this or other studies indicates a potential health hazard to subjects
4. Plans to modify or discontinue the development of the study drug

In the event of Merck decision to no longer supply study drug, ample notification will be provided so that appropriate adjustments to subject treatment can be made.

## 6.0 TRIAL FLOW CHART

### 6.1 Study Flow Chart

Trial Period:	Screening Phase		Treatment Cycles a								End of Treatment	Post-Treatment		
	Pre-screening (Visit 1)	Main Study Screening (Visit 2)	1	2	3	4	To be repeated beyond 8 cycles					Safety Follow-up	Survival Follow-Up	
Treatment Cycle/Title:							5	6	7	8				
Scheduling Window (Days):		-28 to -1		± 3	± 3	± 3	± 3	± 3	± 3	± 3	At time of Discon	30 days post discon	Every 12 weeks	
Administrative Procedures														
Pre-screening Consent	X													
Informed Consent		X												
Inclusion/Exclusion Criteria		X												
Demographics and Medical History	X													
Prior and Concomitant Medication Review	X													
Trial Treatment Administration			X	X	X	X	X	X	X	X				
Post-study anticancer therapy status												X	X	
Survival Status						X					X	X	X	X
Clinical Procedures/Assessments														
Review Adverse Events	X	X	X	X	X	X	X	X	X	X	X	X	X	X
Full Physical Examination		X												
Directed Physical Examination	X		X	X	X	X	X	X	X	X				
Vital Signs and Weight	X	X	X	X	X	X	X	X	X	X				
ECOG Performance Status	X	X	X	X	X	X	X	X	X	X				
Laboratory Procedures/Assessments: analysis performed by LOCAL laboratory														
Pregnancy Test – Urine or Serum β-HCG 	X	X	X	X	X	X	X	X	X	X				
PT/INR and aPTT		X				X					X			
CBC with Differential		X	X	X	X	X	X	X	X	X				

Trial Period:	Screening Phase		Treatment Cycles a							End of Treatment	Post-Treatment		
	Pre-screening (Visit 1)	Main Study Screening (Visit 2)	1	2	3	4	To be repeated beyond 8 cycles				Discon	Safety Follow-up	Survival Follow-Up
Treatment Cycle/Title:							5	6	7	8			
Scheduling Window (Days):		-28 to -1		± 3	± 3	± 3	± 3	± 3	± 3	± 3	At time of Discon	30 days post discon	Every 12 weeks
Comprehensive Serum Chemistry Panel		X	X	X	X	X	X	X	X	X			
Urinalysis		X				X				X			
T3, FT4 and TSH		X				X				X			
Efficacy Measurements													
Tumor Imaging			X		X		X		X		X		
Tumor Biopsies/Archival Tissue Collection/Correlative Studies Blood													
Archival or Newly Obtained Tissue Collection			X			X							
Exploratory Biomarker Blood Collection			X				X				X	X	
Anti-Drug Antibodies and Serum Banking			X	X	X						X		

a only in women of child bearing potential

## **7.0 TRIAL PROCEDURES**

### **7.1 Trial Procedures**

The Trial Flow Chart - Section 6.0 summarizes the trial procedures to be performed at each visit. Individual trial procedures are described in detail below. It may be necessary to perform these procedures at unscheduled time points if deemed clinically necessary by the investigator.

Furthermore, additional evaluations/testing may be deemed necessary by the Sponsor and/or Merck for reasons related to subject safety. In some cases, such evaluation/testing may be potentially sensitive in nature (e.g., HIV, Hepatitis C, etc.), and thus local regulations may require that additional informed consent be obtained from the subject. In these cases, such evaluations/testing will be performed in accordance with those regulations.

